11.3 Secondary Objectives Analysis

Superiority of aQIV vs QIV (higher threshold) (Objective 2a)

To demonstrate that aQIV induces a superior immune response (*higher threshold*) compared to QIV in subjects 50-64 years of age as measured by HI GMT for at least one of 4 vaccine strains at 3 weeks after vaccination. aQIV will be considered to be superior to QIV if, for at least one vaccine strain at Day 22, the following statistical criteria are met:

- *Superior immune response will be demonstrated if the UL of the two-sided 98.73% CI for inter-group GMT ratio (QIV/aQIV) <0.67 for one or more vaccine strains.*

The statistical hypotheses to be tested for the secondary immunogenicity 2a correspond to:

- $H_0: GMTr_i \geq 0.67$, for all four vaccine strains at Day 22
- $H_a: GMTr_i < 0.67$, for one or more vaccine strains at Day 22

where $GMTr_i$ is the Day 22 GMT ratio of GMT_{QIV}/GMT_{aQIV} for one of the four vaccine strains.

Persistence of immune response of aQIV compared to QIV (Objective 2b)

To demonstrate greater persistence of the immune response for at least one vaccine strain at 6 months after vaccination with aQIV compared with QIV as measured by HI assay in subjects 50-64 years of age. aQIV will be considered to be superior to QIV if, for at least one vaccine strain at Day 181, the following statistical criteria are met:

- *Superior immune response will be demonstrated if the UL of the two-sided 98.73% CI for inter-group GMT ratio (QIV/aQIV) <1 for one or more vaccine strains.*

The statistical hypotheses to be tested for the secondary immunogenicity 2b correspond to:

$H_0: GMTr_i \geq 1$, for all four vaccine strains at Day 181

$H_a: GMTr_i < 1$, for one or more vaccine strains at Day 181

where $GMTr_i$ is 6-month GMT ratio of GMT_{QIV}/GMT_{aQIV} for any of the four vaccine strains.

Secondary objective analysis 2a, 2b will be carried out using the same model for GMT ratio analysis as specified for the primary objective analysis at Day 22. Endpoints at Day 22, and Day 181 for objective 2a and 2b will be tested sequentially, each at 0.0127% two-sided significance level.

To evaluate the immunogenicity of aQIV compared with QIV as measured by HI in subjects 50-64 years of age (Objective 2c)

Secondary immunogenicity endpoints 2c include the measures of immunogenicity of aQIV and QIV as determined by the HI assay against homologous strains at Day 1, Day 22, and Day 181 (unless indicated otherwise), include the following:

- GMT of HI antibodies on Day 1, Day 22, and Day 181
- Geometric mean fold increase (GMFI): The geometric mean of the fold increase of post- vaccination HI titer over the pre-vaccination HI titer (Day 22/Day 1, Day 181/Day 1)
- The percentage of subjects with a HI titer $\geq 1:40$ at Day 1, Day 22, and Day 181
- SCR: the percentage of subjects with either a pre-vaccination HI titer $< 1:10$ and a postvaccination HI titer $\geq 1:40$ or a pre-vaccination titer $\geq 1:10$ and a ≥ 4 -fold increase in postvaccination titer on Day 22, and Day 181

Unadjusted Estimates for GMTs, GMFIs, and pertaining 2-sided 95% CIs will be calculated assuming a log-normal distribution of the titers and will be completed by providing minimum, maximum, and median titers for each vaccine group. Binary data (i.e., percentages of subjects with seroconversion and percentage of subjects with a HI titer $\geq 1:40$) will be summarized for each group using crude estimates and will be reported together with 2-sided 95% CIs calculated according to Clopper's and Pearson's method (Clopper and Pearson 1934).

The immune response profiles and subgroup analyses by age cohort, previous vaccination history for the A/H1N1, A/H3N2, B/Yamagata, and B/Victoria strains in the aQIV and QIV groups will be graphically displayed by visit using reverse cumulative distribution (RCD) curves. The RCD curves display titer levels (x-axis) by the percentage of subjects (y-axis) having a titer value greater than or equal to the value on the x-axis.

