2.2 Secondary Objectives

2.2.1 Secondary Immunogenicity Objective(s)

- 2a. To demonstrate that aQIV induces a superior immune response compared with QIV in subjects 50-64 years of age as measured by HI GMT for at least one vaccine strain at 3 weeks after vaccination.

¹ In case of lack of agglutination or agglutination mediated through neuraminidase for a specific strain using HI assay, immunogenicity for that strain will be assessed as measured by microneutralization (MN) assay as an acceptable alternative.

² The GMT ratio is defined as the geometric mean of the post-vaccination HI titer for QIV over the geometric mean of postvaccination HI titer for aQIV.

³ The SCR is defined as the percentage of subjects with either a pre-vaccination HI titer $< 1:10$ and a post-vaccination HI titer $\geq 1:40$ or a pre-vaccination HI titer $\geq 1:10$ and a ≥ 4 -fold increase in postvaccination HI titer. Difference in SCR is defined as $SCR_{QIV} - SCR_{aQIV}$.

Statistical Analysis Plan, Protocol Number V118_23
20OCT2022 Final Version 1.0

Success criteria:

Superior immune response will be demonstrated if the UL of the two-sided 98.73% CI for inter-group GMT ratio (QIV/aQIV) < 0.67 for one or more vaccine strains.

- 2b. To demonstrate greater persistence of the immune response for at least one vaccine strain at 6 months after vaccination with aQIV compared with QIV as measured by HI in subjects 50-64 years of age.

Success criteria:

Greater persistence of the immune response will be demonstrated if the UL of the two-sided 98.73% CI for inter-group GMT ratio (QIV/aQIV) < 1.0 for one or more vaccine strains.

- 2c To evaluate the immunogenicity of aQIV compared with QIV as measured by HI in subjects 50-64 years of age.

2.2.2 Secondary Safety Objective:

To assess the safety and reactogenicity of aQIV and QIV in adults 50-64 years.

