8.4 Multiple Comparisons and Multiplicity

Adjustment for multiple comparison and multiplicity is reflected in the CI of the success criteria, which kept the type I error under 5%. For secondary endpoint analyses, sequential testing and significance level adjustment will be applied to keep type I error under 5%.

For four out of four strain successes, with $\alpha=0.05$ for each strain, the overall type I error is $\alpha^4=0.00000625$.

For two out of four strain successes, with $\alpha=0.05$ for each strain, the overall type I error is $0.05^4+4 \times 0.05^3 \times 0.95+6 \times 0.05^2 \times 0.95^2=0.014019$.

For 1 out of four strain successes, with $\alpha=0.05$ for each strain, the overall type I error is $1-0.95^4=0.1855$.

Thus, for objective 1b): two out of four strain success, there is no need to adjust for $\alpha=0.05$ to keep the overall type I error under 0.05. But for objectives 2a) and 2b): 1 out of four strain success, α needs to be adjusted to 0.01274 so that the overall type I error = $1-(1-0.01274)^4=0.0499944$ which is less than 0.05. Therefore, the CI for the secondary objectives 2a and 2b have been adjusted to 98.73% to keep overall family wise error rate (FWER) under 0.05.

Confirmatory flow of tests and objectives, using a hierarchical testing approach

[figure not shown]
As soon as any success criterion is not met, confirmatory testing will stop.

PRIMARY OBJECTIVE 1a: Non-inferiority	
Tests using Antibody titer at Day 22: UL of 95% CI for GMT ratio (QIV/aQIV) for strain $i \leq 1.5$ and UL of 95% CI for SCR difference (QIV-aQIV) for strain $i \leq 10\%$, for all i , $i = 1$ to 4	Multiplicity consideration: not required, overall type I error is $< \alpha$, where $\alpha = 0.05$
	Analysis Set: PPS
Criterion: UL \leq threshold for all 8 CIs \Rightarrow Non-inferiority confirmed and continue testing	

PRIMARY OBJECTIVE 1b: Superiority for at least 2 strains - basic threshold	
Tests using Antibody titer at Day 22: UL of 95% CI for GMT ratio (QIV/aQIV) for strain $i < 1.0$, for at least 2 out of 4 strains	Multiplicity consideration: not required, overall type I error is $< \alpha$ Analysis Set: FAS
Criterion: CI UL $<$ threshold for at least 2 out of 4 strains \Rightarrow Superiority (basic threshold) confirmed and continue testing	

SECONDARY OBJECTIVE 2a: Superiority for at least 1 strain - higher threshold	

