Tests using Antibody titer at Day 22: UL of 98.73% CI for GMT ratio (QIV/aQIV) for strain $i < 0.67$, for at least 1 out of 4 strains	Multiplicity consideration: α -adjusted CI Analysis Set: FAS
Criterion: CI UL $<$ threshold for at least 1 strain \Rightarrow Superiority (higher threshold) confirmed and continue testing	

SECONDARY OBJECTIVE 2b: Persistence for at least 1 strain - Day 181	
Tests using Antibody titer at Day 181: UL of 98.73% CI for GMT ratio (QIV/aQIV) for strain $i < 1.0$, for at least 1 out of 4 strains	Multiplicity consideration: α -adjusted CI Analysis Set: FAS
Criterion: CI UL $<$ threshold for at least 1 strain \Rightarrow Persistence at Day 181 confirmed and continue testing	

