11.4 Sequential Testing and Significance Levels

As described in section 8.4, the following test procedure will be used to keep the FWER at 2-sided 5% for primary and secondary hypotheses:

- Test hypothesis 1a) (noninferiority) and hypothesis 1b) (superiority) sequentially at 2-sided level of 5%.
- Only after the goal of hypothesis 1a) is achieved hypotheses 1b) will be tested at $\alpha=0.05$ level.

- Only after the primary goals 1a) and 1b) are achieved, the secondary hypotheses will be tested sequentially at $\alpha=0.05$ level.
- For secondary objectives, if both primary objectives are achieved, then 2a will be tested at alpha-0.01274 level (two-sided) for each strain.
- If hypothesis 2a is successful, then hypothesis 2b will be tested at alpha=0.01274 for each strain at Day 181.

The study is considered successful if the primary objective 1a (non-inferiority) is achieved.

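### SAP 11.3 gives the test level for objectives 2a and 2b as 0.0127%, a unit error that contradicts the 98.73% CI criteria in the same section

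*SAP*

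**What the plan says.** SAP 11.3 sets the success criteria for both confirmatory secondary objectives through confidence limits. Objective 2a (Day 22) requires the "UL of the two-sided 98.73% CI for inter-group GMT ratio (QIV/aQIV) <0.67 for one or more vaccine strains". Objective 2b (Day 181) requires the "UL of the two-sided 98.73% CI for inter-group GMT ratio (QIV/aQIV) <1 for one or more vaccine strains". After the two sets of hypotheses, the section adds that the endpoints "will be tested sequentially, each at 0.0127% two-sided significance level".

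The level is also given elsewhere:

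- SAP 2.2.1 uses a two-sided 98.73% interval for 2a and for 2b.
- SAP 8.4 derives the level: alpha "needs to be adjusted to 0.01274 so that the overall type I error" over four strains stays just under 0.05. Both of its decision boxes, for 2a and 2b, use the "UL of 98.73% CI for GMT ratio (QIV/aQIV) for strain" i.
- SAP 11.4 says that if both primary objectives are met, "then 2a will be tested at alpha-0.01274 level (two-sided) for each strain". It gives the same value per strain for 2b.
- Protocol 8.4.2.3.3 gives 0.0127, as a proportion with no percent sign. Protocol 2.2.1, 8.2.2.3 and 8.4.3.3.1 use the 98.73% interval.

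**The concern.** A 98.73% interval corresponds to a two-sided level of 0.0127, which is 1.27%. The sentence in SAP 11.3 attaches a percent sign to the proportion and so states a level 100 times smaller. The section then holds two incompatible instructions for the same two tests.

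This sentence is the only place in SAP 11.3 where the level is written as a significance level and not as an interval. Someone programming the tests or drafting the report from that section could copy it. Objective 2a would then be harder to meet. Because testing is hierarchical, a failed 2a stops confirmatory testing before 2b, and 2b would itself face the stricter level.

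The error cannot produce a false claim, because the literal level is stricter than the intended one.

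**Working it through.** **Which level the plan's own derivation supports.** SAP 8.4 computes the overall error for success on at least one of four strains:

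- At 0.01274: 1 − (1 − 0.01274)^4 = 0.0499944, the figure that SAP 8.4 prints.
- At the Protocol's 0.0127: 1 − (1 − 0.0127)^4 = 0.04984.
- At the literal SAP 11.3 level: 1 − (1 − 0.000127)^4 = 0.00051, about 0.05%, far from the 5% that the derivation aims at.

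These follow the SAP's own convention, which takes the two-sided level as each strain's error rate and uses a product form that treats the strains as independent. What is confirmed here is the arithmetic.

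**Interval and critical value.** 1 − 0.9873 = 0.0127, two-sided z = 2.492. 0.0127% = 0.000127, interval 99.9873%, two-sided z = 3.832.

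**Effect on 2a if the sentence were followed.**

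Inputs:
- SAP 5, Table 2: A/H3N2 log10 difference (aQIV minus QIV) 0.26, SD 0.61; 1,816 evaluable subjects, so 908 per arm.
- The 2a threshold of 0.67 for QIV/aQIV.
- The analysis is a covariate-adjusted model (SAP 8.1 and 11.2), so its residual SD may be below the planning SD. The values 0.55, 0.50 and 0.45 are assumptions that show a range; they are not in the documents.

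Formulas (normal approximation):
- Planned ratio: 10^(−0.26) = 0.55.
- Distance to the threshold: 0.26 + log10(0.67) = 0.26 − 0.1739 = 0.0861.
- SE = SD × √(2/908).
- Power = Φ(0.0861/SE − z).
- Upper limit if the planned ratio is observed = 10^(−0.26 + z × SE).

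| Residual SD | SE | 0.0861/SE | Power, 98.73% CI | Power, literal level | Upper limit, 98.73% CI | Upper limit, literal level |
|---|---|---|---|---|---|---|
| 0.61 (planning) | 0.02863 | 3.007 | 70% | 20% | 0.648 | 0.707 |
| 0.55 (assumed) | 0.02581 | 3.335 | 80% | 31% | 0.637 | 0.690 |
| 0.50 (assumed) | 0.02347 | 3.668 | 88% | 43% | 0.629 | 0.676 |
| 0.45 (assumed) | 0.02112 | 4.076 | 94% | 60% | 0.620 | 0.662 |

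With the intended interval, the planned ratio meets the 0.67 threshold in every row. At the literal level it fails at SD 0.61, 0.55 and 0.50 and passes at 0.45. The break-even residual SD is 0.0861 / 3.832 / √(2/908) = 0.479.

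The other strains add essentially nothing to 2a power. Their planned ratios, 10^(−0.14) = 0.72 for B and 10^(−0.07) = 0.85 for A/H1N1, lie above 0.67. The documents give no Day 181 planning values, so 2b is not quantified.

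**The case against.** The strongest reply is that this is a stray percent sign with nothing operational at stake. Success on 2a and 2b is decided by a confidence limit, and the 98.73% level stands twice in SAP 11.3 itself as well as in SAP 2.2.1 and 8.4 and throughout the Protocol. SAP 11.4, the section devoted to significance levels, gives 0.01274 per strain. A programmer would have to override the criteria in the same section to apply 99.9873%. This is right, and it is why the point is minor. It does not make the sentence correct.

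Three further points deserve an answer:

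- **The power figures are hypothetical.** They apply only to a literal reading, three of the four SDs are assumed, and the plan states no power target for 2a. All true: they size the consequence and show no breach of a design commitment.
- **0.01274 is not exactly 98.73%.** 1 − 0.01274 = 98.726%. The difference is rounding (z of 2.491 against 2.492), and both values keep the SAP's nominal overall error below 0.05. Either may be used in the correction.
- **SAP 11.4 could also be tidied.** It prints a hyphen where an equals sign belongs before 0.01274 for 2a. It also refers to sequential testing of the secondary hypotheses at 0.05, which makes sense only as the level for the family of strains. Neither changes the level applied to each strain.

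**Conclusion.** The concern holds as a minor correction. The level in SAP 11.3 is wrong as written: it is 100 times stricter than the level used in every other statement of the criterion, and it contradicts the two criteria in its own section. The intended level is not in doubt, and the arithmetic behind it in SAP 8.4 reproduces.

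If the sentence were applied literally, power for 2a would fall from 70% to 20% at the planning SD of 0.61, and from 94% to 60% at an assumed residual SD of 0.45. These figures rest on the A/H3N2 planning difference, 908 evaluable subjects per arm and a normal approximation. The error is in the conservative direction. Objectives 1a and 1b are unaffected, as is the rule that the study succeeds on 1a alone.

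**What to change.** In SAP 11.3, replace the level in that sentence so that it reads: each at a two-sided significance level of 0.01274 per strain (98.73% CI). This matches SAP 8.4 and 11.4 and adds the per-strain qualifier that the sentence lacks. Writing 0.0127, as the Protocol does, would serve equally well. The hyphen in SAP 11.4 can be corrected in the same edit.

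The cost is one phrase in the SAP, with no change to design, sample size or analysis.

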11.4 Sequential Testing and Significance Levels

As described in section 8.4, the following test procedure will be used to keep the FWER at 2-sided 5% for primary and secondary hypotheses:

- Test hypothesis 1a) (noninferiority) and hypothesis 1b) (superiority) sequentially at 2-sided level of 5%.
- Only after the goal of hypothesis 1a) is achieved hypotheses 1b) will be tested at $\alpha=0.05$ level.

- Only after the primary goals 1a) and 1b) are achieved, the secondary hypotheses will be tested sequentially at $\alpha=0.05$ level.
- For secondary objectives, if both primary objectives are achieved, then 2a will be tested at alpha-0.01274 level (two-sided) for each strain.
- If hypothesis 2a is successful, then hypothesis 2b will be tested at alpha=0.01274 for each strain at Day 181.

The study is considered successful if the primary objective 1a (non-inferiority) is achieved.

11.5 Exploratory Objectives Analysis

Exploratory objective analysis - to evaluate persistence of the immune response at 9 months after vaccination with aQIV compared with QIV as measured by HI in subjects 50-64 years of age - will be carried out in a similar fashion as for secondary endpoint 2b and 2c after receiving Day 1 retest and Day 271 sera sample testing results. All exploratory analysis results will be presented with 95% CI when applicable. The analysis and result will be included in the CSR addendum. If there is insufficient Day 1 serum sample for retesting, the Day 1 retest data will be considered missing: the original Day 1 result will not be imputed in the exploratory analysis of persistence at Day 271.

Exploratory objective analysis - to further evaluate the immunogenicity of aQIV compared with QIV in subjects 50-64 years of age, with alternative assays, if sera permit - will be carried out in a similar fashion as secondary endpoint 2c.

Exploratory immunogenicity endpoints that may be assessed in the study include the measures of immunogenicity of aQIV and QIV as determined by the HI, the MN or any alternative assay against homologous or heterologous strains at Day 1, Day 22, Day 181, and Day 271 (depending on availability of adequate sera and on assay availability).

Exploratory analysis objective might be specified in an SAP addendum if performed.

12. EFFICACY ANALYSIS

Not applicable

13. SAFETY ANALYSIS

The analysis of safety assessments in this study will include summaries of the following categories of safety data collected for each subject:

- Vaccine exposure
- Solicited local and systemic AEs and other indicators of reactogenicity
- Unsolicited AEs
- Serious AEs, AEs leading to withdrawal, and AESIs

13.1 Analysis of Extent of Exposure

The frequencies and percentages of subjects vaccinated will be summarized overall, by vaccine group and by age group. Data will be tabulated for the All-Exposed Set.

13.2 Solicited Local and Systemic Adverse Events

Solicited AEs are reported daily from Day 1 up to and including Day 7 post-vaccination. If a solicited local or systemic AE continues beyond day 7 after vaccination, recording in the Subject eDiary will be continued until the event(s) resolved or for a maximum of 14 days after vaccination. If the reaction continues to be present on Day 14, the event and follow-up is to be captured as an unsolicited AE in the eCRF. A solicited AE will be defined as “present” or at least mild on any of the recorded days to be counted. This will be summarized as total and for local, systemic and the other category (use of analgesics/antipyretics) separately. The same tables will be created at each time point.

Frequencies and percentages of subjects reporting an AE will be presented overall and for each maximum symptom severity and by vaccine group. Post-vaccination solicited AEs reported from Day 1 to Day 7 will also be summarized for the intervals Day 1-3 and Day 4-7 overall and for each maximal severity and by vaccine group.

Each solicited AE is to be assessed for 7 days following the vaccination according to a defined severity grading scale; see specifics of the solicited event and grading system below in Table 5.

Table 5 Severity Grading for Solicited Local and Systemic Adverse Events

Solicited Local Adverse Event	Grade 1/Mild	Grade 2/Moderate	Grade 3/Severe
Injection site pain	No interference with daily activity	Interferes with daily activity	Prevents daily activity
Erythema	25-50 mm	51-100 mm	>100 mm
Induration	25-50 mm	51-100 mm	>100 mm
Ecchymosis	25-50 mm	51-100 mm	>100 mm
Solicited Systemic Adverse Event	Grade 1/Mild	Grade 2/Moderate	Grade 3/Severe
Loss of appetite	Eating less than usual with no effect on normal activity	Eating less than usual /interfered with normal activity	Not eating at all
Nausea	No interference with daily activity	Interferes with daily activity	Prevents daily activity
Fatigue	No interference with daily activity	Interferes with daily activity	Prevents daily activity
Myalgia	No interference with daily activity	Interferes with daily activity	Prevents daily activity
Arthralgia	No interference with daily activity	Interferes with daily activity	Prevents daily activity
Headache	No interference with daily activity	Interferes with daily activity	Prevents daily activity
Chills	No interference with daily activity	Interferes with daily activity	Prevents daily activity
Vomiting	1-2 times per 24 hours	3-5 times per 24 hours	6 or more times per 24 hours or requires intravenous hydration
Diarrhea	2-3 loose stools per 24 hours	4-5 loose stools per 24 hours	6 or more loose stools per 24 hours or requires intravenous hydration
Fever	38.0-38.4°C	38.5-38.9°C	≥39.0°C

Note: presence of an event on a day is defined as mild, moderate, or severe; absence is defined as none. For Ecchymosis, Erythema and Induration: grading will be derived from the actual measurements in mm; Fever will be derived from the actual measured body temperature.

The use of analgesics/antipyretics will be captured as “absent” or “present” separately by reason “for treatment” or “for prevention”.

The analyses will encompass various summaries of the data by vaccination:

1. Overall summary of subjects with solicited AEs
2. Solicited local AEs, maximum event severity by event and interval
3. Solicited systemic AEs, maximum event severity by event and interval

4. Number of days of solicited AEs, including ongoing AE after Day 7
5. Daily reports of subjects with solicited AEs
6. Day of first onset of solicited AEs
7. Solicited AEs ongoing after Day 7
8. Distribution of maximum body temperature
9. Other use of analgesics/antipyretics

All tables are run by vaccine group.

1. Overall summary of subjects with solicited adverse events.

Any solicited AE presence is defined as at least one day recorded a presence of a local or a systemic AE. No solicited AE is defined as for all days ‘No’ for all pre-defined solicited AEs. Same convention is used considering local and systemic events separate.

The use of analgesics/antipyretics will be considered in this summary as a separate category under “other”, however will be considered for summaries showing “any solicited AE”.

2. Solicited local adverse events, maximum event severity by event and time interval

The maximum event severity will be defined if there is at least one plausible non- missing observation (excluding implausible values) within this time interval. Each subject’s data will be aggregated across the time points of the interval and summarized according to the maximal severity observed for each local AE, followed by a summary across subjects.

The time intervals will be Day 1 to Day 7, Day 1 to Day 3 and Day 4 to Day 7. A summary tables will be created with the frequency for all grade of AEs.

3. Solicited systemic adverse events, maximum event severity by event and interval

The analysis on the maximum severity of the systemic AEs will be done along the same methods as for the local solicited AEs.

4. Number of days with solicited adverse events

The number of days with the AE is defined irrespective of severity. If a solicited AE symptom occurs more than 7 days, it will be counted into the “>7 days” category.

The frequency distribution of the number of days will be provided in a summary table by AE.

5. Daily reports of solicited adverse events

For each day, only subjects with at least one plausible observation (i.e., any non-missing values but excluding implausible values) for the solicited AE will be considered. Data collected will be

summarized (frequencies and percentages of subjects) by vaccine group, solicited AE and time point.

6. Day of first onset of solicited adverse events

The day of first onset is defined, for each subject, for each solicited AE, as the time point at which the respective solicited AE first occurred. The summary will provide the frequencies and percentages of subjects with first onset of each solicited AE by vaccine group and by each time point (i.e., by day).

7. Solicited adverse events ongoing after Day 7

For each of the solicited AEs, the number of subjects that reported the event ongoing after Day 7 (AE present prior or on Day 7 and beyond) will be summarized. Severity grading of solicited AEs that are reported from Day 8 up to Day 14 will be reported in listings only.

8. Distribution of maximum body temperature

Body temperature will be summarized by 0.5 °C increments from 36.0 °C up to ≥ 40 °C by frequency tables.

The following conversion rule is used for the conversion of temperature to °C, and the result is rounded to 1 decimal:

Temperature in °Celsius = (Temperature in °Fahrenheit - 32) *5/9.

9. Use of analgesics/antipyretics

The use of antipyretics and analgesics will be summarized by type of use (prophylactic versus treatment) as the number and percentage of subjects reporting at least one day of use during Day 1-7.

